All data will be checked for out-of-range values, and distributional forms (normality, homogeneity of variance). Decisions regarding parametric vs nonparametric statistics will be based on the results of those analyses. Standard summary statistics will be provided for pre, post- and follow-up time points. The intention-to-treat (ITT) principle will be applied whereby all randomized patients who complete the baseline assessment will be analyzed according to their assigned interventions. For studying the relationship between longitudinal outcomes and NIR stimulation effects, we will fit linear mixed effects models with subject specific random effects to account for the within subject correlation, using R software *lmer* package¹⁵⁸. Linear mixed model is robust against missing data if they are missing at random (MAR)¹⁵⁹. Baseline outcomes and covariates including age, sex, education, and other potential confounders (listed in Exploratory Aim 3) will be adjusted to take account for confounding effects. If multiple hypotheses are investigated simultaneously, multiple comparisons will be properly adjusted by using Benjamini-Hochberg correction¹⁶⁰. Below we describe how these statistical models fit the specific aims in this proposal.

Analyses for Aim 1: To test the hypothesis that the active NIR stimulation will result in greater pre-post intervention improvement in cognition (episodic memory, executive function) relative to the sham group, we will fit the following linear mixed model:

$$y_{ik} = \mu + \alpha_i + \beta \mathbb{I}(z_i = 1) + \sum_{l=0}^L \gamma_l x_{il} + \eta \mathbb{I}(k = 2) + \theta \mathbb{I}(z_i = 1, k = 2) + \varepsilon_{ik}, \alpha_i \sim N(0, \sigma_0^2), \varepsilon_{ik} \sim N(0, \sigma^2) \quad (1)$$

where y_{ik} is the outcome variable (e.g., ARENA score for Aim 1) for subject i and visit k ($k = 1$ for post-intervention and $k = 2$ for 3-month follow-up); μ is the intercept term; $\alpha_i \sim N(0, \sigma_0^2)$ is the random effect with variance term σ_0^2 for subject i ; z_i is the treatment indicator with $z_i = 0$ for sham group and $z_i = 1$ for active

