stimulation group, β is the post intervention treatment effect (active stimulation effect compare to sham group) and $\mathbb{I}(\cdot)$ is the indicator function which equals to 1 if the argument inside (\cdot) is true and equals 0 otherwise; x_{il} is the l^{th} covariates for subject i with $l = 0$ for baseline level (e.g. baseline ARENA for Aim 1) and $l = 1, 2, \dots, L$ for L covariates (i.e., age, sex, education...); η is the time effect of 3-month follow-up compared to post-intervention visit; θ is the interaction effect between follow-up and active stimulation; $\varepsilon_{ik} \sim N(0, \sigma^2)$ is the error term with variance σ^2 . In equation (1), β is the active stimulation effect for post-intervention, and we will perform the statistical hypothesis testing ($H_0: \beta = 0$) to provide its p-value, point estimate and confidence interval. Similarly, $\beta + \theta$ is the active stimulation effect after 3-month follow-up, where p-value, point estimate and confidence interval will be similarly obtained by testing the null hypothesis $H_0: \beta + \theta = 0$. Note that equation (1) will be applied to all measures in Aim 1 including the primary outcome (ARENA), secondary outcomes (working memory), and other exploratory outcomes (verbal fluency, mnemonic similarity, auditory verbal learning test, and Stroop color word test).

Analyses for Aim 2: To test the hypothesis that NIR stimulation will result in greater pre-post intervention improvement in neuroimaging (31P MRS for ATP and rs-fMRI for connectivity) relative to the sham group, we will fit the following linear mixed model:

$$y_{ik} = \mu + \alpha_i + \beta \mathbb{I}(z_i = 1) + \sum_{l=0}^L \gamma_l x_{il} + \varepsilon_{ik}, \alpha_i \sim N(0, \sigma_0^2), \varepsilon_{ik} \sim N(0, \sigma^2) \quad (2)$$

Equation (2) is similar to equation (1), with the adjustment of the same set of covariates, except that the equation (2) doesn't have the 3-month follow-up. β is the active stimulation effect for post-intervention, for which we will perform the statistical hypothesis testing ($H_0: \beta = 0$) to provide its p-value, point estimate and confidence interval. Note that equation (2) will be applied to all measures in Aim 2 including secondary outcomes involving ATP from 31P MRS (H2.1) and connectivity from, rs-fMRI (H2.2).

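### Equation (1) fits one residual variance and one baseline slope to both post-baseline visits, so the primary and 3-month standard errors are miscalibrated in opposite directions if the visit variances differ

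*SAP*

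**What the plan says.** In the SAP, Statistical Analysis, the general statement is that "we will fit linear mixed effects models with subject specific random effects to account for the within subject correlation". Under Analyses for Aim 1, equation (1) sets this out:

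- The outcome is indexed by visit, with k = 1 "for post-intervention and $k = 2$ for 3-month follow-up". Baseline is a covariate, not a visit.
- The subject term "is the random effect with variance term" sigma_0^2, and the residual "is the error term with variance" sigma^2. Neither variance carries a visit index.
- Among the covariates, the index l = 0 stands "for baseline level (e.g. baseline ARENA for Aim 1) and" the higher indices for age, sex, education and so on. Each covariate has one coefficient, used at both visits.
- Two terms separate the visits. Eta "is the time effect of 3-month follow-up compared to post-intervention visit", and theta lets the treatment effect change between them.

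Both effects are tested from this one fit. Beta "is the active stimulation effect for post-intervention, and we will perform the statistical hypothesis testing"; beta + theta "is the active stimulation effect after 3-month follow-up, where p-value, point estimate and confidence interval will be similarly obtained". The same equation serves ARENA, working memory and the exploratory cognitive outcomes.

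The SAP and Protocol section 8.2b plan a check of variance homogeneity, but its only stated consequence is a choice between parametric and nonparametric methods. Protocol section 8.3 leaves room for further analyses without naming any. Neither document plans a visit-specific variance, an unstructured covariance, a baseline-by-visit term or a robust standard error.

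**The concern.** A random intercept with a constant residual variance assumes that scores scatter equally around the fitted line at both visits. That need not hold. The first visit directly follows 12 weeks of treatment; the second comes three months later and is the third sitting of the ARENA task. Baseline may predict the two scores unequally well, and the spread of scores may rise or fall. Equation (1) averages the two residual variances and applies the average to both contrasts.

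At stake are the confidence interval and p-value of the primary effect, and those of the 3-month effect, on which any statement about persistence would rest. The point estimates are not at stake: under randomisation with complete data both remain unbiased.

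**Working it through.** **The plan's own figure.** The sample size is driven by the smallest effect in the SAP, d = 0.48 (prefrontal ATP). With a two-sided 5% test and 80% power, n = 2 x (1.960 + 0.842)^2 / 0.48^2 = 68.1, so 69 per group, and 69 / 0.85 = 81.2, so 82 after 15% attrition. The t-test version gives 70, then 83. The stated 84 per group reproduces to within two. About 168 x 0.85 = 143 patients, or 71 per group, are then analysed.

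**Inputs for the check.** The structure is that of equation (1). Correlations of baseline with the post score (r1) and with the 3-month score (r2) are assumed, as is the ratio s of the 3-month SD to the post SD. Baseline and post SDs are set to 1.

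**Formulas, complete pairs.** The true slopes are b1 = r1 and b2 = r2 x s. The fitted common slope is g = (b1 + b2)/2. The true residual variances around that slope are v1 = 1 - 2 g b1 + g^2 and v2 = s^2 - 2 g b2 + g^2. The model reports (v1 + v2)/2 at both visits, so reported SE / true SE = sqrt[((v1 + v2)/2) / v_k]. The size of a nominal 5% test is 2 x [1 - Phi(1.96 x ratio)].

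Worked case r1 = 0.7, r2 = 0.5, s = 1: g = 0.60; v1 = 1 - 0.84 + 0.36 = 0.52; v2 = 1 - 0.60 + 0.36 = 0.76; mean 0.64. The ratios are sqrt(0.64/0.52) = 1.109 and sqrt(0.64/0.76) = 0.918.

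**Equal SDs (s = 1), with test size in brackets:**

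| r1 / r2 | v1, v2 | Post-intervention | 3-month |
|---|---|---|---|
| 0.6 / 0.6 | 0.640, 0.640 | 1.00 (5.0%) | 1.00 (5.0%) |
| 0.6 / 0.5 | 0.6425, 0.7525 | 1.04 (4.1%) | 0.96 (5.9%) |
| 0.7 / 0.6 | 0.5125, 0.6425 | 1.06 (3.8%) | 0.95 (6.3%) |
| 0.7 / 0.5 | 0.520, 0.760 | 1.11 (3.0%) | 0.92 (7.2%) |
| 0.7 / 0.4 | 0.5325, 0.8625 | 1.14 (2.5%) | 0.90 (7.8%) |

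**Unequal SDs.** At 0.7/0.5 with s = 1.2 the ratios grow to 1.25 and 0.86. At 0.7/0.6 with s = 0.85 they reverse to 0.977 (5.6%) at post and 1.025 (4.5%) at 3 months. The errors cancel at s of about 0.82 for 0.7/0.5, 0.89 for 0.7/0.6 and 0.92 for 0.6/0.5; below those values the direction reverses.

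**Which restriction matters.** At 0.7/0.5 a free slope would leave a post residual variance of 1 - 0.49 = 0.51, against 0.52 with the common slope. The slope restriction costs about 1% in SE (sqrt(0.52/0.51) = 1.010); the rest comes from pooling the variance.

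**Simulation.** 4,000 trials at 0.7/0.5 with equal SDs, 84 per group and 15% dropout gave, at post, a true SE of 0.120 against 0.134 reported (size 2.9%). At 3 months the true SE was 0.144 against 0.134 reported (size 6.3%). With dropout only before the 3-month visit the ratios were 1.10 and 0.91, and the 3-month size was 7.4%. Separate covariance analyses per visit, standing in for the corrected model, gave sizes of about 4.5-5.7% across the scenarios run.

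**Power of the primary test** at 0.7/0.5, equal SDs and 71 per group, with the effect in outcome-SD units, equation (1) against the per-visit analysis: 62% against 71% at 0.30; 87% against 92% at 0.40; 96% against 98% at 0.48. The pilot's d = 1.06 is in units of the SD of change. At r1 = 0.7 that is 1.06 x sqrt(2 - 1.4) = 0.82 outcome SDs, where z = 0.82/0.121 - 1.96 x 1.109 = 4.6, and no power is lost.

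**The case against.** The strongest reply is that the documents supply neither correlations nor visit SDs, so nothing shows that the visit variances will differ. The participants are screened as cognitively normal, and a fall in correlation from 0.7 to 0.5 over three further months is an assumption. Milder falls do little: 0.7/0.65 gives 3% too wide at post and a 3-month test size of 5.7%; 0.6/0.55 gives 2% and 5.5%. The direction is open too. ARENA is a learning task with a 120-second cap, and the Protocol expects practice effects, so a smaller spread at the third sitting is plausible. All of this stands, and it limits what can be claimed about size and direction.

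It also stands that hypotheses H1.1 and H1.2 concern the 12-week change. The 3-month contrast has a planned test but no stated hypothesis of its own.

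The reply that variance heterogeneity is already covered does not stand. The homogeneity check leads only to a parametric or nonparametric choice, and no remedy for unequal visit variances is named.

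A reader might infer that the primary analysis is biased, that its false-positive rate is inflated, or that the 3-month result is bound to be anti-conservative. The documents support none of these. The estimates are unbiased with complete data; in the equal-SD cases with a falling correlation the primary test is conservative; and the direction turns on SDs that are not reported.

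**Conclusion.** The restriction is plain in equation (1): with complete pairs, both effects receive the same standard error whatever the visit variances are. If the residual variances differ, confidence intervals and p-values err in opposite directions at the two visits.

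How far they err is conditional. Over the tabulated range, and with the SD unchanged between visits, the loss falls on the primary interval and the anti-conservative error on the 3-month test. Some dropout before the post visit softens the latter. Power for the primary test suffers materially only if the true effect is well below the pilot value, which rests on 8 active and 5 sham participants. A sufficiently smaller 3-month SD exchanges the two errors.

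The point is confined to Aim 1. Equation (2) has a single post-baseline visit, so there is nothing to pool. It is a matter of calibration, not a flaw that invalidates the primary analysis. It is worth correcting because the sponsor cannot know in advance which case applies and the correction is nearly free.

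**What to change.** Before unblinding, amend equation (1) in two ways:

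1. Replace the random intercept and common residual variance with an unstructured 2x2 covariance across the two visits. This is the main correction; a slope term alone would leave most of the error in place.
2. Add a baseline-by-visit term, with baseline centred, so that beta and beta + theta keep their present meaning.

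State Kenward-Roger or Satterthwaite degrees of freedom.

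The SAP names lmer, which is not suited to this. An unstructured random-effect covariance plus its residual variance is four parameters for three identifiable moments. Name instead an R function that allows visit-specific residual variances, either a repeated-measures mixed model or generalised least squares.

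The cost is revised model wording, a different fitting function and two or three extra parameters with about 143 patients analysed. If the visit variances turn out equal, almost nothing is lost. It is a free improvement.

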7.5.2 Imaging Outcome Measures (Secondary) (Aim 2)

All participants will undergo a standard neuroimaging protocol before and after the NIR intervention. We plan to focus on cerebral mitochondrial function (**31P MRS ATP**) and resting state functional connectivity (**rs-fMRI**). The first imaging outcome is change in ATP, one of the key mechanisms associated with NIR stimulation. We plan to use a single voxel method for MRS to achieve optimal sensitivity and will measure from two ROIs (temporal, frontal), corresponding to our primary (memory) and secondary (executive) cognitive outcomes from Aim 1. The second imaging outcome involves changes in rs-fMRI connectivity which will enable us to document system level network brain changes.

Neuroimaging Protocol. Imaging will be performed on the AMRIS 3T Siemens Prisma MRI systems at UF and a 3T Siemens Skyra at UA. Inside the brain scanner, participants will lie on a padded table with foam pads used to hold the participants head in place. Participants will be asked to lie as still

as possible. There will be no specific task or behavior that the participant must engage in. We anticipate that this protocol may take up to 1.5 hours.

The protocol will be optimized for standardized acquisition for structural (e.g., T1, T2, etc.), functional (resting state fMRI), and magnetic resonance spectroscopy (phosphorous MRS). We will apply the ADNI-3 scanning sequences using a standard Siemens head coil and 31P MRS sequences on a dual-tuned whole head phosphorous coil (RapidMRI). Specifics are detailed below.

MRI. Whole brain axial gradient-echo MPRAGE T1-weighted images will be acquired for 31P and fMRI localization (~6 minutes duration). 2D/3D FLAIR imaging will be acquired, time allowing within the 1.5 hour scan, to assess white matter hyper-intensity load (~6 minutes duration). High resolution hippocampal imaging will be performed, time allowing within the 1.5 hour scan, to allow localization of

MRI Sequences			
Run	Sequence	Domain Assessed	Min(s)
1	T1/MPRAGE	Structure	6:20
2	3D FLAIR	White matter hyperintensities	5:30
3	Hippocampal	Hippocampal subfield measurement	4:20
4	T2* GRE	Cerebral microbleed assessment	4:10
5	ASL	Cerebral perfusion	4:00
6	Diffusion	White matter integrity	7:30
7	EPI-BOLD	Resting State	10:00
-	Coil Change	Change 32-channel coil for 31P coil	10:00
8	31P MRS	Frontal ATP and 31P metabolites	10:00
9	31P MRS	Left temporal ATP and 31P metabolites	10:00
			Total Time
			71:50

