8.3. Statistical Analyses

For hypotheses associated with Aims 1 (cognitive) and 2 (imaging), we plan to conduct linear mixed effects models and other potential analyses. For Aim 3, we are interested in predictors of treatment responses and will explore a variety of potential mediators and/or moderators including APOE-4 carrier status, vascular comorbidities (including white matter burden), mood/emotion, processing speed, and demographic variables. To examine confounders, we will directly adjust these variables as covariates in a linear mixed model. Additional analyses will be conducted as appropriate.

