8.4. Methodological Limitations

Few previous human studies have conducted sham controlled trials. Thus, there is a potential impact of placebo in producing positive effects on cognition. The current study attempts to control for this. Another issue pertains to the penetrance of near infrared light through the skull. Most transcranial NIR light applied to the human cranium penetrates 1 cm into the tissue, reaching cortical tissue but not white matter or subcortical structures. As a result, the dosage reaching particular brain structures depends on a variety of factors such as cranium thickness, degree of cortical atrophy, penetrance, source of light, and duration of treatment/energy density of light.

9. Study Time Line Schedule of Activities

The Schedule of Participant Activities for this study is as follows:

- Call #1- Telephone Prescreening to review the study details, and inclusion/exclusions.

- **Informed Consent Process and Screening Visit**- Informed Consent Process begins with the participant per UF, state and federal guidelines. Once the participant has signed the informed consent, complete medical history, inclusion/exclusion criteria, concomitant medications, and cognitive and mood questionnaires will be administered (listed in section C). The screening evaluation will take up to 1.5 hours. If participant formally meets study criteria, then he or she is invited to participate in the intervention phase of the study consisting of baseline, NIR stimulation, and post-baseline testing.
- **Baseline Assessment** - This assessment involves a series of computer based measures and other questionnaires, along with a brain scan and blood draw. This cognitive and mood assessment may take up to 5 hours and may be broken up across days, if necessary. The brain imaging will take between 60-80 minutes and the blood draw approximately 30 minutes.

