Analysis for Exploratory Aim 3: We want to further explore whether APOE $\varepsilon 4$ carrier status, vascular comorbidities, Fitzpatrick skin type questionnaires, processing speed, and mood are potentially confounders, moderators, or mediators. To examine confounders, we will directly adjust these variables as covariates in the linear mixed model in equation (1) and equation (2). A statistically significant covariate effect will imply the potential confounding roles of these variables. To examine moderators, we will include these variables and their interactions with the intervention effect (one variable at one time) in equation (1) and equation (2). A statistically significant interaction effect will imply the variable can be a moderator. To examine mediators, we will perform mediation analysis¹⁶¹⁻¹⁶². The mediation effects of these variables and their 95% confidence interval will be determined using the R *mediation* package¹⁶³.

For each of the specific aims listed above, we will further conduct exploratory analysis stratifying by sex, to examine its relevant biological effect. In other words, we will disaggregate the data by sex and evaluate the active stimulation effects for male and female, respectively.

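### The SAP puts the Exploratory Aim 3 variables into the primary and secondary models but has no rule for a missing covariate, so randomised participants with outcome data can be dropped

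*SAP*

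**What the plan says.** **Covariates, general rule.** The SAP's Statistical Analysis section says "Baseline outcomes and covariates including age, sex, education, and other potential confounders (listed in Exploratory Aim 3) will be adjusted". The sentence stands before the aim-specific models and is not limited to exploratory work.

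**Covariates, equation (1).** The covariate sum is described as "covariates (i.e., age, sex, education" followed by an ellipsis, so the list is left open. The SAP adds that "equation (1) will be applied to all measures in Aim 1 including the primary outcome (ARENA" and the other Aim 1 measures. Equation (2), for the imaging outcomes, takes the same covariates.

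**Covariates, Aim 3.** The SAP's Aim 3 paragraph asks whether APOE e4, vascular comorbidities, skin type, processing speed and mood are "potentially confounders, moderators, or mediators". It looks for confounding by adding them to equations (1) and (2). White matter load is not on this list. It comes in only through the protocol: Section 6 names it under the Exploratory Aim, and Section 8.3 refers to "vascular comorbidities (including white matter burden), mood/emotion, processing speed, and demographic variables".

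**Where the values come from.** APOE comes from a blood sample (protocol Section 7.5.3a). White matter load comes from a sequence described in Section 7.5.2: "2D/3D FLAIR imaging will be acquired, time allowing within the 1.5 hour scan, to assess white matter hyper-intensity load".

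**Analysis set and missing data.** Under the SAP's intention-to-treat rule, "all randomized patients who complete the baseline assessment will be analyzed according to their assigned interventions". Its only missing-data statement is that the mixed model is robust under missing at random. Protocol Section 8.2b says data will be checked for missingness but gives no rule for handling it.

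**The concern.** The robustness that the SAP relies on concerns missing outcomes. A likelihood-based mixed model uses whatever visits a participant has, but it cannot use a row in which a covariate is blank, and the software's default is to omit that row. The Aim 3 covariates are one value per participant, so a single missing value removes every visit of that participant. Someone with baseline and post-intervention ARENA scores but no genotype would leave the primary test, although the intention-to-treat rule says that person will be analysed.

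Two things are at stake. First, the population of the primary analysis would depend on measurements that the primary question does not need. Second, the primary model would not be fixed in advance: one passage requires the adjustment and another treats it as exploration. Randomisation already deals with confounding of the treatment comparison, so its validity does not rest on these variables.

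**Working it through.** **1. Side-by-side reading.** The general rule puts the Aim 3 variables in every model. The Aim 3 paragraph adds the same variables to the same equations as a further step, which would be redundant if they were already there. Both cannot describe the primary model. Neither document has an imputation rule, a missing-indicator rule or any other rule for a blank covariate.

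**2. Reproducing the planned sample size.** Inputs from the SAP: smallest effect d = 0.48 (prefrontal ATP), 5% alpha, 80% power, 15% attrition. The protocol's sample size paragraph (Section 7.2) makes the test two-tailed. A two-sample t-test needs 70 per arm, and 70 / 0.85 = 82.4, rounded up to 83. The stated 84 per arm agrees. Expected completers are 84 × 0.85 = 71.4 per arm, or 142.8 in total.

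**3. ARENA.** The SAP's d is 1.06 (0.58 / 0.55 = 1.05, consistent with rounded inputs). At 71.4 per arm power exceeds 99.9%. If half of the completers were lost (35.7 per arm), it would still be 99.3%.

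**4. Prefrontal ATP.** The documents give no rate of missing covariates, so the last three rows of the table rest on assumed, independent rates for FLAIR / APOE / all others:
- 3% / 2% / 2%: 0.97 × 0.98 × 0.98 = 0.932, and 71.4 × 0.932 gives 66 per arm
- 5% / 3% / 3%: 0.95 × 0.97 × 0.97 = 0.894, giving 63
- 10% / 5% / 3%: 0.90 × 0.95 × 0.97 = 0.829, giving 59

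The SAP's effect sizes are for change scores, whereas equation (2) adjusts for the baseline value. With equal variances before and after and a baseline-to-post correlation r, the adjusted residual variance is (1 + r)/2 of the change-score variance. The effective d is then 0.48 / √((1 + r)/2), which is 0.492 at r = 0.9 and 0.521 at r = 0.7. The values of r are assumptions.

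| Per arm | Change score | Adjusted, r = 0.9 | Adjusted, r = 0.7 |
|---|---|---|---|
| 71 | 81.1% | 83.0% | 86.9% |
| 70 | 80.5% | 82.5% | 86.4% |
| 69 | 79.9% | 81.9% | 85.9% |
| 66 | 78.1% | 80.2% | 84.3% |
| 63 | 76.2% | 78.3% | 82.6% |
| 59 | 73.4% | 75.6% | 80.1% |

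On the SAP's own change-score basis, losing a second participant per arm takes prefrontal ATP just below the promised 80%. With baseline adjustment the slack is larger, by an amount that depends on r.

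**The case against.** The strongest reply is that the Aim 3 paragraph is exploratory and that the primary model means age, sex, education and the baseline outcome. That reading is possible, but the general rule says otherwise, and on either reading the set has to be fixed in one place.

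Several stronger readings are tempting, and the documents do not support them:

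- **Optional FLAIR imaging decides who is in the primary analysis.** The SAP's list does not name white matter load. Protocol Section 6 treats it separately from vascular risk, and only the parenthesis in Section 8.3 merges them. In the Section 7.5.2 schedule FLAIR is run 2 of 9, and the total of 71:50 leaves about 18 minutes within 1.5 hours. In that order, a scan that ran out of time would lose the phosphorus spectroscopy first.
- **The intention-to-treat wording itself removes many participants.** Protocol Section 9 says of the baseline visit "This assessment involves a series of computer based measures and other questionnaires, along with a brain scan and blood draw". But Section 7.5 places this testing before randomisation, and inability to be scanned is an exclusion. The wording probably removes few randomised participants, if any.
- **Post-treatment mood or speed would adjust part of the effect away.** Section 6 speaks of baseline factors, and the covariate term in equation (1) has no visit index. The SAP calls these variables possible mediators, but neither document plans to put post-treatment values in the primary model.
- **Missing APOE will be common.** Blood is drawn twice and genotype does not change, so a second sample could supply a missing result, although the plan is to genotype at baseline.

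**Conclusion.** The concern holds in a limited form. As written, the SAP makes the Aim 3 variables covariates in the primary and secondary models, contradicts this in tone in its Aim 3 paragraph, and has no rule for a missing value. Followed literally with lmer's default, it drops randomised participants who have outcome data.

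The consequences are a departure from the stated intention-to-treat set and some loss of precision. A reader might infer that the ARENA result would be biased or underpowered. Neither follows. Exclusion on a covariate whose missingness is settled before randomisation does not by itself bias the treatment comparison, and ARENA power stays above 99% at the planned effect even under a 50% loss.

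The power exposure is confined to the ATP outcomes, chiefly prefrontal ATP. Its size is unknown because it rests on assumed missingness and on the unstated gain from baseline adjustment. This is a correction worth making before unblinding, but it does not put the trial's primary conclusion in doubt.

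**What to change.** State the covariate set for the primary and secondary tests once: the baseline value of the outcome analysed, age, sex, education and the factors actually used in randomisation. Those factors must first be reconciled, because protocol Section 7.2 gives age, education and gender while Section 8.2a gives age and MoCA. Delete the parenthetical reference to Exploratory Aim 3 from the SAP's general covariate sentence, so that those variables enter only the Aim 3 models.

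Alternatively, if the Aim 3 variables are kept, say that baseline values only are used, and fill missing ones by mean imputation with a missing indicator, so that no randomised participant with outcome data is dropped.

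Optionally, define the intention-to-treat set by having a baseline value of the outcome analysed, rather than by a completed baseline assessment.

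The cost is SAP wording. The first option gives up whatever precision prognostic Aim 3 covariates might have added; the second keeps it at the price of a slightly larger model.
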